The proposed study is a randomized controlled trial of an educational intervention to improve glaucoma medication adherence. Participants will be Veterans who are patients of the Durham VA Eye Clinic with medically-treated glaucoma and their companions (family or friend) if a companion is available (we have been approved for a Waiver of Informed Consent Documentation for companions). Participants will be randomized to receive either a general eye health educational session (control arm) or an educational intervention developed to improve glaucoma medication adherence (intervention arm). All participants will be provided with a "smart bottle" (AdhereTech, NYC) to house one of their glaucoma medications. The smart bottle records the date and time that the bottle is opened. For participants in the intervention arm only, a reminder through AdhereTech will be activated. Participants randomized to the intervention will meet with the interventionist approximately 4 weeks following the enrollment visit. The intervention will be delivered one-on-one, in a private room at the Durham VA. Companions, if applicable, will accompany the Veteran in the intervention. Drop administration instruction will be directed toward the veteran participant or if applicable towards the companion. Veterans randomized to the control arm will be scheduled for a session with the interventionist approximately 4 weeks after the enrollment visit. The control visit will include review of a Powerpoint presentation on general eye health, including but not specific to glaucoma. The presentation will be delivered one-on-one, in a private room at the Durham VA. Companions, if applicable, will accompany the Veteran in the presentation. Both the intervention and the control session will last approximately 30-60 minutes. Participants in the control arm will receive an electronic medication monitor but the reminder function will not be activated. Participants will be brought in for a 6-month follow up visit and the 12 month follow up will be conducted over the telephone.

Outcomes:

Specific Aim 1. Evaluate the impact of an intervention to improve glaucoma medication adherence among Veterans at 6-month follow up.

Hypothesis 1: Veterans randomized to the intervention will have a greater proportion of prescribed glaucoma medication doses taken as measured by the electronic medication monitor in the 6 months following the intervention compared to Veterans randomized to the control arm.

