Control Arm Content: The control arm is designed as an attention control that includes interaction with the interventionist. This will allow us to attribute observed differences to the content of the intervention, rather than increased interaction with a provider. Veterans randomized to the control arm will be scheduled for a session with the interventionist approximately 4 weeks after the enrollment visit. The information session will be delivered one-on-one in a private room in the Durham VA. The control visit will include review of a Powerpoint presentation on general eye health, including but not specific to glaucoma. The control session will last approximately 60 minutes, similar in length to the time spent in the intervention. Participants in the control arm will receive an electronic medication monitor but the reminder function will not be activated. Companions, if applicable, will accompany patient participants to the educational session.

6 month Study Visit: At approximately 6 months after randomization, we will schedule a follow up appointment with both control and intervention arm participants. We will have participants bring back their Adhere Tech bottles and participants will be compensated \$20. At the 6-month study visit we will administer the SASES survey, the NEHEP survey as well as ask about any intermittent life events; we will observe eye drop administration and if the companion is responsible for drop administration, drop administration observation will be directed towards the companion.

12 month Study Visit: At approximately 12 months following initial intervention visit we will call participants and administer the SASES survey, the National Eye Institute Visual Function Questionnaire survey, EuroQol as well as ask about any intermittent life events. We may call participant and/or companion after the 12 month study visit to ask follow up questions on their experience in our research study.

Table 1:
Timetable of Data Collected from Patients and Companions

Patient Participant Measures	Baseline	Ed Session	6 months	12 months
Demographics: Age, sex, race, ethnicity, education, marital status, living environment, self-rated health	X			
General: Rapid Estimate of Health Literacy in Adults ⁶³	X			
Self-reported glaucoma medication adherence: Self-reported Adherence and Self-efficacy Survey (SASES)	X		X	X
EuroQoI (EQ-5D5L)	X			X
EuroQoI EuroQoI				
Intermittent Events: Stressful life events, Changes in vision			X	X

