Direct Intervention Arm Cost. The main intervention costs are labor inputs, consisting of the one-time fixed labor cost of training and the variable labor cost of conducting the adherence intervention. To calculate training cost, we will multiply [name] and the ophthalmic technician's respective wage rates, including fringe benefits cost, by the 3 hours needed for training. Training cost will be applied in the base-case analysis, but because training cost attenuates over time as more patients are treated, it will be excluded in sensitivity analysis. For each one-on-one session and monthly booster phone calls with the patient/companion, the

interventionist will log the session and phone call times. These times will be multiplied by the technician's wage rate to estimate intervention variable labor cost. The non-labor cost inputs will consist of the smart bottles and eye drop aids provided to patients. The fixed training, variable intervention labor and non-labor inputs will be aggregated and then divided by the number of patients in the intervention arm to derive per-patient intervention cost.

Direct Control Arm Cost. Time of each one-on-one session with the patient/companion will be logged and multiplied by the technician's wage rate to estimate per-control patient cost.

Indirect cost. The VA healthcare system also incurs costs, such as administration, utilities, and custodial services that cannot be directly attributed to a given health care service but nonetheless should be included in the cost analysis. We will collect direct and indirect costs observed for ophthalmology clinic stop codes in the VA Decision Support System (DSS) extract for the Durham VA Medical Center. These will be used to calculate a direct-to-indirect cost multiplier. This multiplier will be applied to the estimated direct intervention and control arm costs to estimate their respective total costs. For both intervention and control arm costs, we will only account for costs that are likely to be incurred in "real world" clinical care; study-driven costs will be excluded. For example, the education session provided to control arm patients isn't likely to occur in usual clinical care and will not be included in the cost estimate.

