these ratios by replicating the Markov model developed by the Centre for Eye Research Australia.⁶⁸ We will use 2nd order Monte Carlo simulation to incorporate probabilistic sensitivity analysis into the base-case estimates and to estimate confidence intervals of the incremental cost-effectiveness ratios. We will also conduct extensive parameter and model sensitivity analyses to assess the robustness of the base-case results. If the main outcome is not statistically significant between the two groups, then the economic analysis will focus on differences in intervention costs and health care costs between the two groups during the study period.

Budget and Workflow Impact. For planning purposes it will be helpful for VA administrators to know what impacts implementing this adherence intervention will have on budget and workflow. We will use US glaucoma prevalence information available in the literature⁶⁹ to extrapolate the number of Veterans that are likely to be affected by glaucoma annually. We will multiply this target patient population by the intervention and health care resource utilization costs observed first by the treatment arm patients and then by the control arm patients. The difference between these 2 estimates will be the incremental budget impact of the intervention. Similarly, we will multiply this target patient population by the amount of per-patient time required to conduct the intervention in the treatment and control arms and the incremental time will be the workflow impact. We will convert the incremental workflow impact to full-time equivalents (FTEs).

1. Kingman S. Glaucoma is second leading cause of blindness globally. *Bulletin of the World Health Organization* 2004;82:887-8.

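### The Aim 3 workflow estimate may subtract control-session time that the plan excludes only as a cost, understating staffing need by up to one control session per patient

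*Combined protocol and SAP*

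**What the plan says.** All references are to the combined protocol and SAP.

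- **Budget and Workflow Impact** (data analysis section, Specific Aim 3). For workflow, the plan will "multiply this target patient population by the amount of per-patient time required to conduct the intervention in the treatment and control arms". The incremental time is the workflow impact, and it is then expressed in FTEs. The stated purpose is to help VA administrators plan for adoption of the intervention.
- **Direct Control Arm Cost.** The time of each control session is logged and multiplied by the technician's "wage rate to estimate per-control patient cost". The economic section logs no other control-arm staff time.
- **Indirect cost.** Only costs expected in real-world care count, and "study-driven costs will be excluded". The control session is the worked example: it is not "likely to occur in usual clinical care and will not be included in the cost estimate". Both statements concern cost; neither mentions time or workflow.
- **Direct Intervention Arm Cost.** Logged intervention time covers the one-on-one session and "monthly booster phone calls with the patient/companion". The length of the calls is not given, and they do not appear under Intervention Arm Content or in Table 1.
- **Session length.** Under Design: "Both the intervention and the control session will last approximately 30-60 minutes". Under Control Arm Content: "The control session will last approximately 60 minutes, similar in length to the time spent in the intervention".
- **Comparator for Aim 3.** It is usual care in the Outcomes section and control in the data analysis section.

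**The concern.** The control session exists for a trial reason. Control Arm Content says of the attention control: "This will allow us to attribute observed differences to the content of the intervention, rather than increased interaction with a provider". Staff contact is therefore meant to be about equal in the two arms. That suits the efficacy comparison, but it makes the control arm a poor stand-in for usual care when the question is how much staff time a clinic must find. A clinic that adopts the program does not save a control session, because it never gave one.

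The plan recognizes this for money and removes the session from cost. For time, it names the control arm as a term in the subtraction and does not repeat the exclusion. An analyst who looks for a control-arm time finds one logged quantity, the control session. Entering it would leave little beyond booster calls as the workflow impact of a program built on a one-on-one session of 30-60 minutes. It would also set the two halves of one paragraph against each other: the budget impact would carry the intervention labor in full, while the workflow impact would net off most of the same hours.

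**Working it through.** The plan states no per-patient time result, no size for the target population and no hours per FTE, so there is no figure of its own to reproduce. The check is direct arithmetic on minutes per patient.

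**Inputs**
- I, intervention session: 30-60 min (Design).
- C, control session: 30-60 min (Design), or about 60 min (Control Arm Content).
- B, total booster-call time per patient: not given. Values of 0, 30 and 60 min are assumed, only to show whether B matters.
- R, existing technician education that the session would replace: not given. The Interventionist paragraph says that technicians already carry some or all of patient education. Values of 0, 15 and 30 min are assumed.

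**Step 1. The two versions of the rule**
- Logged control time subtracted: I + B - C.
- Control time counted as zero: I + B.
- Difference: (I + B) - (I + B - C) = C, whatever I and B are.

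**Step 2. Numbers (minutes per patient)**

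| I | C | B (assumed) | I + B - C | I + B | Difference |
|---|---|---|---|---|---|
| 30 | 30 | 0 | 0 | 30 | 30 |
| 30 | 30 | 30 | 30 | 60 | 30 |
| 60 | 60 | 0 | 0 | 60 | 60 |
| 60 | 60 | 30 | 30 | 90 | 60 |
| 60 | 60 | 60 | 60 | 120 | 60 |
| 30 | 60 | 0 | -30 | 30 | 60 |
| 60 | 30 | 0 | 30 | 60 | 30 |

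When the sessions are equally long, as the design intends, the subtraction leaves B alone. If the control session ran longer, the result could even be negative.

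**Step 3. Allowing for education already given**

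Against usual care, the relevant increment is I + B - R. The shortfall from subtracting C is then (I + B - R) - (I + B - C) = C - R. With C at 30-60 min:
- R = 0: 30 to 60 min.
- R = 15: 15 to 45 min.
- R = 30: 0 to 30 min.

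One full control session is therefore the upper limit. By the same algebra, counting control time as zero gives I + B, which exceeds the usual-care increment by R.

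**Step 4. No FTE figure**

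A conversion would need the target population and the hours per FTE. The documents give neither, so the size is left in minutes per patient.

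**The case against.** The strongest reply is that the plan already means zero control time. Several features support it:

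- The workflow sentence counts time needed to conduct the intervention. The control arm does not receive the intervention, so that time could be read as zero. The usage is not firm, however: the Educational Session paragraph also uses the word intervention for the session that both arms attend.
- The sentence opens by likening itself to the budget calculation just before it, which is subject to the real-world rule.
- Labor cost is logged time multiplied by a wage. Dropping a session's cost as study-driven arguably drops its time.
- The paragraph after Hypothesis 3 in the Outcomes section feeds cost and labor-time data together into one budget and workload estimate.
- A rule that returns almost nothing by design is unlikely to be what the authors intended.

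These points stand as evidence of a plausible intention. They do not close the gap. If control time were always zero, there would be no need to name both arms and take an increment. No sentence carries the exclusion over to time, and the two comparator wordings point in different directions.

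Two further objections stand in full. The shortfall reaches a whole session only if the new session is wholly additional to existing education. And this is a descriptive planning output without a hypothesis test, with times logged by arm, so either version can still be computed after the data are in.

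A reader might infer something stronger: that the plan demonstrably understates staffing by 30-60 minutes per patient, or that the budget impact is distorted in the same way. The documents do not support either. The first depends on a reading that the text permits but does not compel, and on full additionality. The second is answered by the Indirect cost paragraph, which expressly removes the control session from cost.

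**Conclusion.** This is a minor point: a rule that can be applied in two ways, one of which defeats its stated purpose. Entering the only logged control-arm time is the more natural way to carry out the subtraction as written. It would make the staffing estimate too low by anything up to one control session per patient.

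The limit of 30-60 minutes (or about 60) rests on the stated session lengths and on no replacement of existing education. The shortfall falls as replacement rises, and it is zero if the exclusion was meant to cover time. No percentage shortfall can be given, because booster-call time is unknown.

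The primary adherence analysis and the therapy-intensification analysis do not use this quantity.

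**What to change.** In Budget and Workflow Impact, state that the real-world exclusion under Indirect cost applies to time as well as cost. Control-session time then counts as zero, and workflow impact is the logged intervention-arm time per patient (the session plus any booster calls actually delivered) against usual care. Use the usual-care wording for the Aim 3 comparator in both the Outcomes and the data analysis sections.

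It would also help to say whether the session is assumed to add to or partly replace the education that technicians already give. If it partly replaces it, the reported time should be labeled an upper estimate.

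The cost is a few clauses. Session and call times are already to be logged, so no new data are needed. The small downside is a larger reported staffing need than the subtraction would give, and one that errs high if some existing education is replaced.
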